different activities may deliver positive health benefits to those returning to green social spaces. Adults aged over 45 years have lower levels of distress if they are physically active in greener surroundings, but exposure to green space among those who do no or little activity has no impact on mental health. With social connections severely restricted due to COVID-19, it is important to understand how safe interventions utilizing nature contact/exposure can support mental health and social interactions. This issue is also wider than the current pandemic, with global standards existing for urban spaces to align with the Sustainable Development Goals (SDGs) which include the aim, by 2030, of providing universal access to safe, inclusive and accessible public green spaces, particularly for women and children, older people and people with disabilities. Research on this is limited at present, but evidence suggests exposure to green space can improve sense of belonging and interconnectedness with others in younger cohorts; by logical extension this should follow in other populations, but there is no consensus as to the impacts of nature contact on social connections in older adults.

Our team have developed and piloted a protocol in younger adults (in the UK) to understand how activity type may impact mood. Specifically, we looked at how a 'default activity' in green space (walking in a park) compared to a 'cerebral activity' (citizen science; learning about green space with little to no physical exertion) and 'physical activity' (digging and planting, with little cerebral exertion) to understand green 'dosing'. Using this framework, we seek to understand how different activities might impact older adults in our local community.

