### Answer/Response:

Building on pilot work from our team exploring green space activity type, this study aims to focus specifically on older adults in Charlottesville and the surrounding areas. We aim to understand how green space activity type may influence belonging, loneliness and mood and how this may impact on willingness to return to JABA centers. Our research questions are as follows;

1. What types of green space activities have a beneficial impact on loneliness, belonging and mood in seniors who are JABA center members?
2. Does the inclusion of these activities encourage JABA service users to continue participation at their JABA centers?

To investigate these questions, we will utilize 2 study components. The first, titled 'activity sessions' refers to a participant group who will undergo a series of activities (on separate days) including walking, citizen science and planting in order to understand pre- and post-activity wellbeing. The second component, titled 'survey-only', refers to a different participant group who are remotely surveyed on their current wellbeing, experiences during COVID and barriers on returning to JABA. All participants will be JABA service users.

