## Study Design: Biomedical

### 1. Will controls be used?

Answer/Response: Yes

► IF YES, explain the kind of controls to be used.

Answer/Response: There are two controls. First, during the activity sessions, participants will act as their own control, crossing over to take part in each activity. Second, we also will conduct a survey remotely in which participants will respond to questions regarding their current wellbeing. These will be compared to those of the participants who undergo the activity sessions.

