**4. What is your plan for primary variable analysis?**

UVA Study Tracking: HSR210100

Version Date: 03-22-21

Page Number: 6 of 11

Include primary outcome(s)/predictor variable(s), statistical methods/models/tests to be employed, or descriptive summaries as appropriate. If not applicable, please provide explanation.

**Answer/Response:** We will use the following outcome measures across the study.

- Loneliness; measured by the UCLA Loneliness Scale, a 3-item scale that captures feelings of loneliness. (Activities and survey-only)
- Belonging; measured by the General Belonging Scale (GBS), a 12-item scale capturing social acceptance/inclusion and social rejection/exclusion. (Activities and survey-only)
- Acute Mood; pre and post measures of mood will be taken using the UWIST Mood Adjective Checklist (MACL), an acute measure of hedonic tone, stress and arousal. (Activities only)
- Restoration; Psychological restorative qualities of the setting measured by the Perceived Restorativeness Scale, a three point scale determining the restorative quality of activity spaces. (Activities only)
- Physical Activity; In addition to the arousal measure of the MACL, we will use the 10 point scale of the OMNI Perceived Exertion scale, to understand how physically exerted participants feel between activities. To understand baseline physical activity, we use the international physical activity questionnaire (IPAQ) to compare between studies (Activities and survey-only).
- Accelerometer; we will use accelerometers to measure participant movement throughout the activities to correlate with physical activity measures. (Activities only). Specifically, we will look to understand if increased movement, as measured by the accelerometer, correlates with increased feelings of exertion post-activity (across all three activities).

For measures taken in both the activities and survey-only, we will use an independent t-test using condition (activity or survey) to compare. For activities that use pre- and post-assessments, we will make change scores for each and use this in a one-way ANOVA, using activity type (three levels; walking, citizen science, planting) as the grouping variable.

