**Answer/Response:**

There are two components to this study, so we describe each separately. *Activity sessions*

There will be three activity sessions, the protocol for each is largely the same. For the walking and the citizen science sessions, participants will be transported (Jaunt bus) to a nature preserve to conduct this session. Alternatively, if participants wish to transport themselves, they are welcome to – this will be confirmed after obtaining consent. The planting session is held at the JABA center. Upon arrival at the given site, participants will be given their initial pre-activity survey to complete (pen and paper) and are given an accelerometer to wear throughout the study session. Following this, they will undertake their activity; this will include a short nature walk, a guided citizen science walk or a session planting and tending to greenery in raised beds. At the end of the sessions (up to 30 minutes), participants will complete the post-activity survey and remove their accelerometer. After payment (\$10 supermarket voucher per session), participation ends.

*Survey Only*

Participants are mailed a study information sheet and the the survey with a return envelope. They are asked to complete the survey and return it to the research team.

**1. If this protocol involves study treatment, explain how a subject will be transitioned from study treatment when they have completed their participation in the study.**

**Example:** If the subject will be taking an investigational drug, will they need to be put back on an approved drug when they have completed the study? If yes, explain how this will be accomplished and who will cover the cost. If the subject has a device implanted will it be removed? Again- who will cover the cost of the removal?

**Instructions:** Answer NA if this study does not involve a study treatment.

**Answer/Response:** N/A

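### The crossover has no unexposed period and the only no-activity comparator is non-randomised, pooled and without mood data, so no single activity's benefit can be attributed as research question 1 asks

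*Combined protocol and SAP*

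**What the plan says.** Research question 1 (Objectives/Hypothesis) is: "What types of green space activities have a beneficial impact on loneliness, belonging and mood in seniors who are JABA center members".

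Study Design, question 1, names two controls. In the activity component, "participants will act as their own control, crossing over to take part in each activity". Then: "Second, we also will conduct a survey remotely in which participants will respond to questions regarding their current wellbeing", and "These will be compared to those of the participants who undergo the activity sessions".

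Study Procedures, question 1, describes the sessions: "this will include a short nature walk, a guided citizen science walk or a session planting and tending to greenery in raised beds". Walking and citizen science take place at a nature preserve, planting at the JABA center. On the pre-measure: "Upon arrival at the given site, participants will be given their initial pre-activity survey to complete".

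Statistical Considerations, question 4, sets the analysis. For pre- and post-assessments, "we will make change scores for each and use this in a one-way ANOVA, using activity type" with three levels. Measures shared with the survey-only group are compared by an independent t-test of activity against survey. Mood is collected in the activity component only. Question 1 of that section answers No to randomisation or stratification, question 5 (secondary analysis) is N/A, and no order of activities is stated anywhere.

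**The concern.** Research question 1 is about benefit, which needs a comparison with not doing the activity. Crossing over among three active sessions supplies comparisons among the activities only. Anything that raises mood in every session, such as an outing, company or contact with staff, sits inside each pre-to-post change and cannot be separated from the activity.

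The planned analysis does not close this gap. An omnibus test across three activities asks only whether they differ. It has no reference level and no contrasts, so even a significant result does not say which activity differs from which. It is also a between-groups test applied to the same people measured three times, although the protocol itself calls the design repeated measures.

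At stake is whether the report can say that a given type of activity helps, which is what the research question promises.

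**Working it through.** **Inputs.** From the documents: 60 enrolled, about 10% attrition, 54 completers, 27 per group (Human Participants, Subjects, question 2). Check: 60 × 0.90 = 54, and 54 / 2 = 27, which reproduces. No alpha, SD, effect size or correlation is given. Assumed here: two-sided 5%, SD of a change score 1, correlation ρ between one person's changes in two activities of 0.3 to 0.5.

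**1. What each comparison can identify.**

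| Comparison | Outcomes | No-activity reference? | Separates activities? |
|---|---|---|---|
| Activity vs activity, same person | Mood, and any other pre/post measure | No | Yes |
| Pre to post within a session | Same | No; the pre-measure is taken on arrival at the site | Yes, but uncontrolled |
| Activity vs survey-only | Shared measures, including loneliness and belonging; not mood | Yes, but different people, not randomised | No; one pooled condition |

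No row has both a no-activity reference and separate activities. For mood, no row has a no-activity reference at all.

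**2. Common benefit.** The F statistic depends on the activity means only through their deviations from the grand mean. Adding a constant to all three leaves it unchanged. On one simulated data set (27 people, three activities), F was 0.2185 with common shifts of 0, 0.5 and 5 SD.

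**3. Repeated measures treated as independent groups.** There are 3 × 27 = 81 change scores, so the one-way ANOVA uses F(2, 78), with 5% critical value 3.11. With equal within-person correlation ρ and no true difference:

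- expected between-activity mean square = 1 − ρ;
- expected within-activity mean square = [52(1 − ρ) + 26(1 + 2ρ)] / 78 = 1.

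The ratio is therefore centred near 0.7 (ρ = 0.3) or 0.5 (ρ = 0.5) instead of 1. Simulating these mean squares gives rejection rates of about 1.5% at ρ = 0.3 and 0.4% at ρ = 0.5, against 5.0% at ρ = 0. With positive correlation the planned test is conservative and gives up the precision that the crossover provides.

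**4. Precision of paired contrasts.** The SD of a difference in change is √(2(1 − ρ)), and the half-width is t × SD / √27 on 26 df.

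- ρ = 0.3: SD = √1.4 = 1.183 and SE = 1.183 / 5.196 = 0.228. The 95% half-width is 2.056 × 0.228 = 0.47 SD. Bonferroni for two contrasts gives 2.379 × 0.228 = 0.54 SD; for all three pairs, 2.559 × 0.228 = 0.58 SD.
- ρ = 0.5: SE = 1 / 5.196 = 0.192. The half-widths are 0.40 SD, and 0.46 SD for two contrasts.

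**5. Confounding of the contrasts.** If a difference in site or order alone shifted one activity by 0.2 or 0.3 SD relative to another (assumed), a paired contrast at ρ = 0.3 has noncentrality 0.2 / 0.228 = 0.88 or 0.3 / 0.228 = 1.32. It would then be significant about 14% or 25% of the time with no true activity difference.

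**The case against.** **There is a no-activity control.** A reader might infer that the design can identify nothing but differences between activities. The documents do not support that: the same answer that calls participants their own control names survey-only as a second control, and a t-test against it is planned for loneliness and belonging, two of the three outcomes in research question 1. This stands. It does not rescue the question, because that comparator is not randomised, pools the activities and has no mood data.

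**No before-after test is planned.** A reader might infer a high rate of false benefit claims. If each activity's mood change were tested against zero, a non-activity lift of 0.2 or 0.3 SD (assumed) would be significant about 17% or 32% of the time: a one-sample t with 26 df and noncentrality 0.2√27 = 1.04 or 0.3√27 = 1.56. But the plan states no such test, and the ANOVA it does state is unaffected by a common lift. The figures are a reason to label those changes descriptive, not an error rate of the plan.

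**Contrasts with walking are not automatically clean.** It is tempting to say that a shared lift cancels against walking. It cancels only if it really is shared. Planting has a different site from the other two sessions, and order is neither randomised nor stated.

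**Walking is not named as the control.** The Background calls walking the default activity when describing the team's UK pilot. That framework is carried forward, but the objectives and analysis treat the three activities alike. Walking is a reasonable reference, not one that the protocol requires.

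**It is a pilot sized by feasibility.** True, and the aim is also phrased comparatively, as how activity type may influence the outcomes. But the statistical section gives the pilot's purpose as establishing impacts, and research question 1 asks about benefit.

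**Conclusion.** The concern holds in this form. The within-person component supports comparisons between activities and nothing more. The survey-only comparison adds a weak no-activity reference for loneliness and belonging, none for mood, and none specific to an activity. Followed as written, the plan cannot say which activity is beneficial.

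That conclusion is structural and needs no assumed number. The assumed quantities affect only size: the planned test's rejection rate of about 0.4% to 1.5% at a nominal 5% rests on ρ of 0.5 to 0.3, and the paired half-width of 0.47 SD (0.54 SD for two contrasts) rests on ρ = 0.3 and 27 completers. Intervals of that width suit a pilot but will not separate activities that differ modestly.

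**What to change.** **Statistical Considerations, question 4.** Replace the one-way ANOVA with a within-person analysis: repeated measures or a mixed model with a participant effect. Pre-specify paired contrasts between activities, with 95% confidence intervals and a multiplicity correction. Either take walking as the reference (two contrasts) or use all three pairs, and say which in advance.

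**Objectives and Study Design, question 1.** Limit the mood part of research question 1 to differences between activities. Label pre-to-post changes within a session as descriptive. Label the survey-only comparison of loneliness and belonging as non-randomised and not activity-specific.

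**Limitations.** State that site (planting at the JABA center, the other two at a preserve) and unrandomised order may confound the contrasts.

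**Cost.** Protocol wording and a different analysis of data already planned for collection; no new participants, sessions or measures. The downside is a narrower claim than research question 1 now makes. Two contrasts against walking would also leave citizen science against planting without a formal comparison; using all three pairs avoids that at a half-width of about 0.58 SD instead of 0.54 SD.

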### 2. What is the study design?

Example: case series, case control study, cohort study, randomized control study, single-blind, double-blind, met-analysis, systematic reviews, other. You may also view the IRB-HSR Learning Shot on this topic to help you answer this question.

[https://hrpp.irb.virginia.edu/learningshots/Writing\\_protocol\\_June09/player.html](https://hrpp.irb.virginia.edu/learningshots/Writing_protocol_June09/player.html)

Answer/Response: For the activity sessions, the study is a repeated measures study design. For the survey only group, the study is a single cohort study.

### 3. Does the study involve a placebo?

Answer/Response: No

► IF YES, provide a justification for the use of a placebo

Answer/Response: N/A

## Human Participants

**Ages:** 65 and over

**Sex:** Not controlling for sex, but would prefer 50:50 if possible

**Race:** all

### Subjects- see below

**INSTRUCTIONS:** For question 1-4 below insert an exact #. Ranges or OPEN is not allowed. This # should be the maximum # you expect to need to enroll (i.e. sign consent) If you are only collecting specimens the number of participants should equate to the # of specimens you need. If you are collecting only data from a chart review the

UVA Study Tracking: HSR210100

Version Date: 03-22-21

Page Number: 3 of 11

number should designate the number of subjects whose medical records you plan to review. Age/ Sex/Race criteria should designate the demographics of participants from whom you will obtain the specimen/data.

**1. Provide target # of subjects (at all sites) needed to complete protocol.**

**INSTRUCTIONS:** If this is NOT a database protocol, this number should be the same as the number of subjects needed to obtain statistically significant results.

**Answer/Response:**

60

**2. Describe expected rate of screen failure/ dropouts/withdrawals from all sites.**

**Answer/Response:**

We would expect around 10% attrition, so a final sample of 54 (n = 27 per group) is expected

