**3. Provide a justification for the sample size used in this protocol.**

Include sample size calculations or statistical power estimation. If not applicable, please provide explanation.

Also include the anticipated accrual rate, the accrual goal for the study, including accrual goals by strata if appropriate, adjustments for drop-outs etc. and study duration.

Answer/Response: In collaboration with JABA, an n of 60 across the two study components is a realistic number of participants to be able to recruit.

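### The plan does not say how activity participants who attend only one or two of the three sessions are analysed, and its one-way ANOVA is a poor default for them

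*Combined protocol and SAP*

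**What the plan says.** The activity component is a within-person design. Objectives/Hypothesis describes "a participant group who will undergo a series of activities (on separate days) including walking, citizen science and planting", and Study Design, question 1, says "participants will act as their own control, crossing over to take part in each activity". Study Procedures, question 1, adds: "There will be three activity sessions, the protocol for each is largely the same". Surveys are completed before and after each session.

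Statistical Considerations, question 4, gives the analysis of the pre/post measures: change scores are formed, and the plan is to "use this in a one-way ANOVA, using activity type (three levels; walking, citizen science, planting) as the grouping variable".

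The only statement on loss is in Human Participants, Subjects, question 2: "We would expect around 10% attrition, so a final sample of 54 (n = 27 per group) is expected". The form's prompt there is "Describe expected rate of screen failure/ dropouts/withdrawals from all sites", so the answer is one pooled figure. It also covers the survey-only group, which has no sessions to miss.

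The protocol defines no analysis set and names no missing-data method or sensitivity analysis. It has no rule for a participant with one or two sessions. It does not state the order of the activities; Statistical Considerations, question 1, says only that there is no stratification or randomization.

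**The concern.** A mailed survey is either returned or not. An activity participant can also stop partway, leaving usable pre/post scores from the sessions attended. Two analysts could follow this plan faithfully and treat that person differently:

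- **All available rows.** The one-way ANOVA is run on every change score that exists. The attended sessions stay in, but the three activity means then come from partly different people, and nothing in the model links a person's scores.
- **Completers only.** Only people with all three change scores are analysed, as in a conventional repeated-measures ANOVA. The comparison is then within the same people, but the sessions of anyone who stopped are thrown away.

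In people aged 65 and over, an unrewarding or tiring first session is a plausible reason not to return. If so, the comparison of activities that research question 1 asks for depends in part on an unstated choice. Adding a participant term through a complete-case repeated-measures ANOVA would restore the pairing but would still drop the partial attenders.

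**Working it through.** **Plan's own figure.** 60 × (1 − 0.10) = 54, and 30 × (1 − 0.10) = 27 per group. This reproduces exactly. The 30 per group is implied by 27 per group, not stated. No alpha, power, effect size or SD is given, so there is no power figure to check.

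**Data at stake.** If the 10% applies evenly, 3 of 30 activity participants are lost. Full attendance gives 30 × 3 = 90 change scores. Dropping 3 people leaves 27 × 3 = 81. If all 3 were partial attenders, keeping their attended sessions gives 81 + 3 = 84 (one session each) to 81 + 6 = 87 (two each). So 3 to 6 of the 9 lost scores could be kept.

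**Bias in a worst case.** All of the following are assumptions, not in the documents:
- 30 people, and no true difference between activities;
- change-score SD of 1, with correlation ρ of 0.3, 0.5 or 0.7 between a person's change scores;
- the same activity first for everyone;
- the lowest 10% on that first session stop after it.

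The contrast is the first activity minus the mean of the other two. The mean of the upper 90% of a standard normal is 0.1755 / 0.9 = 0.195. Hence:
- completers-only bias = 0.195 × (1 − ρ);
- available-row bias = −0.195 × ρ.

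The simulation (20,000 runs) removes exactly the lowest 3 of 30:

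| ρ | Completers, formula | Completers, simulated (SE) | Available rows, formula | Available rows, simulated (SE) |
|---|---|---|---|---|
| 0.3 | +0.137 | +0.128 (0.194) | −0.059 | −0.058 (0.193) |
| 0.5 | +0.098 | +0.092 (0.165) | −0.098 | −0.094 (0.165) |
| 0.7 | +0.059 | +0.057 (0.128) | −0.137 | −0.129 (0.130) |

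The signs are opposite. The simulated biases run from about 0.3 of a standard error (0.058 / 0.193) to about 1.0 (0.129 / 0.130). A generalised least squares analysis of all attended sessions under the same set-up was within 0.005 SD of zero. That is expected, because here stopping depends only on an observed score. With milder dependence of stopping on the first score, the biases are about half as large.

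**Same case, balanced order.** With 10 people starting on each activity, the bias was within 0.003 SD of zero under both analyses at every ρ. With no true difference, symmetry gives this result.

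**Precision, with sessions missed at random.** If each session is independently missed with probability 0.10 (an assumption, not the plan's figure), 30 × 0.9³ = 21.9 people attend all three. Relative to a model using all attended sessions with the correct within-person correlation, at ρ = 0.3, 0.5 and 0.7:
- the completers-only contrast has variance ratios of 1.21, 1.20 and 1.19;
- the difference of available-row means has ratios of 1.02, 1.06 and 1.18.

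This scenario costs precision and produces no bias.

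**The case against.** The strongest reply is that this is a self-described pilot, sized by feasibility ("an n of 60 across the two study components is a realistic number of participants to be able to recruit"), with no decision threshold. Only a handful of change scores are in question. The worst-case bias is no more than about one standard error and needs deterministic stopping by the lowest scorers. It also needs one common activity order, which the protocol does not state. All of that stands, and it limits the size of the point. It does not supply the missing rule, and the method that the plan does name suits a crossover with missed sessions poorly.

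Three stronger readings are tempting and are not supported:

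- *The plan excludes partial attenders.* A reader might infer this from the headcount of 27. No section says so, and the ANOVA taken literally would keep their attended sessions.
- *At least 10% of activity participants will be partial attenders.* The text says around 10%. It pools screen failures, dropouts and withdrawals over both components, so it is neither a minimum nor a partial-attendance rate. People who never start have no session data to save.
- *The activity contrast will be biased whenever stopping depends on how a session felt.* That requires the order to be common, or at least unbalanced. The absence of randomization does not show that the order is fixed.

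The protocol also does not say at which session loneliness, belonging and IPAQ are collected. The point is therefore confined to the session change scores.

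**Conclusion.** The gap is real and modest in size. The protocol specifies a three-session within-person design and an analysis that ignores the pairing, and it leaves the handling of partial attenders open. If the activity order is common to everyone and stopping depends on the first session's score, the two natural analyses err in opposite directions. The worst case is about 0.05 to 0.13 SD, with 3 of 30 stopping and ρ of 0.3 to 0.7. With a balanced order and no true difference, the bias is about zero. What remains then is lost precision: about 20% more variance for completers-only if 10% of sessions are missed at random, and less for available rows unless ρ is high. The correlation, the stopping mechanism, the order and the missing rate are all assumptions. The documents show that the choice is open; they do not show that the result will be biased.

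**What to change.** In Statistical Considerations, question 4, replace the one-way ANOVA with a likelihood-based mixed model on all attended-session change scores. Use activity as a fixed effect, session order as a further fixed effect if it varies between people, and participant as a random effect. State that everyone with at least one completed pre/post session is included and that missing a session is not grounds for exclusion. Report a completers-only analysis as a sensitivity check.

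In Human Participants, Subjects, question 2, say what the 27 in the activity group counts. If it is the expected number completing all three sessions, label it so.

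The cost is a few sentences of protocol text and slightly more analysis work, with no added participants or visits. The limitation is that the model is unbiased only if stopping depends on scores already observed; stopping for unrecorded reasons related to the missing scores would not be corrected. If the order turns out to be the same for everyone, activity and session order cannot be separated by this or any other model.
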